11.4. Pharmacokinetic Analyses

Plasma concentrations of JNJ-64179375 will be listed for all subjects by time of collection and dose level. For each dose, descriptive statistics, including mean, median, standard deviation (SD), and coefficient of variation will be calculated for the plasma concentrations at each nominal sampling time. Plasma concentrations of JNJ-64179375 versus time profiles will be plotted for each subject based on actual sampling times, and mean concentration versus time profiles will be plotted for each dose level based on planned sampling times.

Data will be listed for all subjects with available plasma concentrations per treatment group. Subjects will be excluded from the PK analysis if their data do not allow for accurate assessment of the PK (eg, incomplete administration of the study drug; missing information of dosing and sampling times; concentration data not sufficient for PK parameter calculation).

All plasma concentrations below the lowest quantifiable concentration or missing data will be labeled as such in the concentration database. Concentrations below the lower quantifiable concentration will be treated as zero in the summary statistics. All subjects and samples excluded from the analysis will be clearly documented in the study report.

In addition, a population PK model will be developed and the dependence of PK of JNJ-64179375 on population covariates (eg, demographics, laboratory variables) will be evaluated. This will be performed using nonlinear mixed-effects modeling with the software package NONMEM[©]. The mean (and variance) values for specific PK parameters (eg, CL and V_z) will be estimated and the statistical significance of the relationships between the covariates and PK parameters will be evaluated. The results of this population PK (PK parameters signifying relationship between PK and various covariates) analysis will be reported separately, in a document other than the CSR.

11.5. Immunogenicity Analyses

The incidence of antibodies to JNJ-64179375 will be summarized for all subjects who receive a dose of JNJ-64179375 and have at least 1 appropriate sample obtained after study drug administration for the detection of antibodies to JNJ-64179375.

A listing of subjects who are positive for antibodies to JNJ-64179375 will be provided. The maximum titers of antibodies to JNJ-64179375 will be summarized for subjects who are positive for antibodies to JNJ-64179375.

Analyses of the impact of immunogenicity on PK, PD, PK/PD, efficacy, and safety endpoints will be performed to further characterize the immune responses that are generated.

11.6. Pharmacodynamic/Biomarker Analyses

The PD parameters are TT, ECT, PT, aPTT, and D-dimer. Descriptive statistics including mean, median, SD, minimum, and maximum will be provided for the PD parameters. The parameters of TT, PT, and aPTT may be statistically analyzed using mixed models. The mixed model for the change from baseline PD parameters will include dose and visit as fixed effects and subjects as random effects. The least-squares means for change from baseline and associated 95% CIs will be provided. Other PD parameters may be analyzed similarly.

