1.1.2.2.4. Pharmacodynamics

Prothrombin time, aPTT, and TT demonstrated dose-dependent increases whether measured locally or at a central specialty laboratory, with TT being the most sensitive test and PT the least sensitive test. A plot of mean ratio to baseline for TT from the central specialty laboratory is provided in Figure 1. For TT, the 2 highest dose groups showed similar prolongations for the early timepoints (an approximately 7-fold increase) as some subjects in both groups exceeded the laboratory upper reporting limit of 120 seconds. At 14 days, the prolongation in TT was about 5-fold for the highest dose group. At the 0.3-mg/kg dose level, the peak prolongation in TT was

approximately 2.7-fold and it was approximately 1.7-fold at 14 days. For aPTT, the assay upper reporting limit was not approached for any subject but the maximum prolongation appears to be an approximately 1.6-fold increase from baseline for each of the 3 highest dose groups. For PT, the maximum-fold increase was approximately 1.3-fold at the highest dose. These data are consistent with the in-vitro data and with the mechanism of action of JNJ-64179375. Local laboratory results demonstrated a similar pattern.

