1.1.2.2.5. Overall Summary

In this single-ascending dose (SAD), randomized, double-blind, placebo-controlled study in healthy male subjects (Part 1), JNJ-64179375 was generally well tolerated at all doses. All observed bleeding events were of mild or moderate intensity, mostly related to local trauma (eg, venipuncture, brushing teeth, blowing nose), and none were severe or serious. At the 2 highest doses (2.125 and 2.5 mg/kg), an increased frequency (and severity at 2.5 mg/kg) of bleeding events was observed compared with placebo.

With the exception of the bleeding adverse events, there was no evidence of dose-dependent adverse events over the studied dose range. As hypersensitivity reactions have been observed with the administration of monoclonal antibodies, infusion or allergic reactions were closely monitored for this study. One subject in the 2.5-mg/kg cohort developed mild urticaria that started prior to receiving the study drug. The urticaria spread and was assessed as moderate in severity at approximately 4 hours postdose. The urticaria resolved spontaneously 24 hours later and was considered doubtfully related to the study drug.

JNJ-64179375 administered as an IV infusion exhibited a favorable PK profile in healthy subjects, and the observed PK parameters were close to those predicted based on the animal PK data. Mean C_{max} and AUC_{inf} values increased in an approximately dose-proportional manner in the studied dose range. Mean $t_{1/2}$ ranging from 21.8 to 29.2 days is consistent with the expected $t_{1/2}$ of human IgG4. Importantly, variations of the PK concentration and parameters (C_{max} and AUC_{inf}) of JNJ-64179375 were low, indicating PK predictability.

Consistent with the nonclinical findings, JNJ-64179375 produced a dose-dependent prolongation of the coagulation parameters (PT, aPTT, and TT) over the studied dose range. Based on fold-changes from baseline observed in this study, TT was the most sensitive assay for JNJ-64179375, which is consistent with its mechanism of action and direct effect on thrombin-mediated clot formation. The effect-time curves for all coagulation parameters seemed parallel to the plasma drug concentration-time curves of JNJ-64179375 with no apparent lag time.

1.1.2.3. Parts 2 and 3

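### The optional PD mixed model has no dose-by-visit term, so on the raw change scale any least-squares means it gives by dose at each visit would be biased

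*Protocol*

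**What the plan says.** Protocol 11.6 makes the model optional: "The parameters of TT, PT, and aPTT may be statistically analyzed using mixed models". It then gives the terms: "The mixed model for the change from baseline PD parameters will include dose and visit as fixed effects and subjects as random effects". On output it says: "The least-squares means for change from baseline and associated 95% CIs will be provided". It does not say whether these means are by dose, by visit, or by dose at each visit. Separately and without condition, "Descriptive statistics including mean, median, SD, minimum, and maximum will be provided for the PD parameters".

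The Time and Events Schedule places coagulation samples predose, at 1 hour, at Day 10-14 and at Week 5, which gives three postdose visits. Protocol 9.4 does not plan to analyze the apixaban samples, so only JNJ-64179375 doses would enter the model.

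The Phase 1 background in Protocol 1.1.2.2.4 reports TT prolongation at 0.3 mg/kg as "approximately 2.7-fold and it was approximately 1.7-fold at 14 days", the first figure being the peak. For the two highest Phase 1 doses the early value was "an approximately 7-fold increase) as some subjects in both groups exceeded the laboratory upper reporting limit of 120 seconds". Later, "At 14 days, the prolongation in TT was about 5-fold for the highest dose group". Protocol 1.1.2.2.5 adds: "The effect-time curves for all coagulation parameters seemed parallel to the plasma drug concentration-time curves".

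SAP 7.3 (Part 1) states no PD mixed model. SAP 7.4 mentions linear or non-linear mixed models for PK/PD and leaves the detail to a separate document.

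**The concern.** With dose and visit entered additively, the difference between any two doses is the same at 1 hour, Day 10-14 and Week 5. The effect follows concentration, and exposure is roughly proportional to dose (Protocol 1.1.2.2.3), so the gap between doses should instead narrow as drug is cleared. An additive fit spreads the average fall over all doses. It takes too much from the low dose at late visits, leaves too much at the high dose, and flattens the 1-hour peak at the high dose.

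What is at stake is the reading of the PD time course. Change in PD by dose is an exploratory endpoint, and choosing the most suitable assay is an exploratory objective. If dose-at-visit means were reported, a low dose could appear to have lost its effect while still active.

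**Working it through.** The plan states no least-squares mean for this model, so there is no figure to reproduce. The check fits the stated additive form to cell means. With complete data a subject random effect does not alter these fits:

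fitted(dose, visit) = mean for that dose + mean for that visit - grand mean.

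Values are excess over baseline in multiples of baseline, that is, fold minus 1. This treats mean baseline as equal across doses.

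**1. Phase 1 TT figures (Protocol 1.1.2.2.4)**

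- 0.3 mg/kg: 2.7 - 1 = 1.7 at peak and 1.7 - 1 = 0.7 at Day 14, a fall of 1.0.
- Highest dose: 7 - 1 = 6 early and 5 - 1 = 4 at Day 14, a fall of 2.0. The early value was capped by the reporting limit, so the true fall is at least this.
- Dose means: 1.2 and 5.0. Visit means: 3.85 and 2.35. Grand mean: 3.1.
- Fitted at 0.3 mg/kg, Day 14: 1.2 + 2.35 - 3.1 = 0.45, against 0.70. The error is -0.25, and 0.25/0.70 = 36%.
- The other fitted cells are 1.95 (against 1.7), 5.75 (against 6) and 4.25 (against 4). The model imposes a fall of 1.5 at both doses.

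**2. Planned Part 1 doses (0.3, 0.6, 1.2 mg/kg) at three visits, by extrapolation**

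The documents give no Week 5 PD values, so two sets of assumptions were used.

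(a) Effect proportional to dose, anchored on 1.7 and 0.7 at 0.3 mg/kg, with Week 5 = Day 14 value x 2^(-21/half-life). At a 25-day half-life, 0.7 x 0.559 = 0.39.

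(b) Two-phase decline matched to the 0.3 mg/kg row of Protocol Table 3 (Cmax 6.86 µg/mL, AUCinf 145, half-life 26 days) and scaled by dose, with an assumed 3-day initial half-life. The Emax curve has maximum 7.9 and EC50 25 µg/mL, passing through 2.7-fold at 6.9 µg/mL and an assumed 5.2-fold at 28.4 µg/mL.

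| Cell | (a) true | (a) fitted | (b) true | (b) fitted |
|---|---|---|---|---|
| 0.3 mg/kg, 1 h | 1.70 | 2.73 | 1.69 | 2.07 |
| 0.3 mg/kg, Day 10-14 | 0.70 | 0.39 | 0.78 | 0.74 |
| 0.3 mg/kg, Week 5 | 0.39 | -0.33 | 0.41 | 0.07 |
| 1.2 mg/kg, 1 h | 6.80 | 5.52 | 4.12 | 3.76 |
| 1.2 mg/kg, Week 5 | 1.56 | 2.46 | 1.42 | 1.76 |

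For 0.3 mg/kg at Week 5 under (b), the arithmetic is 0.96 + 0.87 - 1.757 = 0.07. Under (a), half-lives from 21.8 to 29.2 days give fitted values of -0.39 to -0.26 against true values of 0.36 to 0.43.

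**3. Means that are not affected**

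Under (a) with balanced data, the means by dose (0.93, 1.86, 3.72) and by visit (3.97, 1.63, 0.91) are the same, true and fitted. With an assumed dose-related loss of samples, the dose means move modestly to 0.87, 1.86 and 3.95.

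**4. Additive model on log ratio to baseline**

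- Phase 1 figures: ln(2.7/1.7) = 0.463 and ln(7/5) = 0.336. The difference is 0.126, and a quarter of it, 0.032, falls on each cell, or about 3%.
- Grid (b): every cell is within about 4% of the true fold ratio. At 0.3 mg/kg, Week 5, it is 1.35 against 1.41.
- Grid (a), 0.3 mg/kg at 1 h: dose mean (0.993 + 0.531 + 0.330)/3 = 0.618; visit mean (0.993 + 1.482 + 2.054)/3 = 1.510; grand mean 1.013. The fit is 0.618 + 1.510 - 1.013 = 1.114 (rounding aside), or 3.05-fold against 2.70, about 13% high and the worst cell.

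**The case against.** The strongest reply is that little depends on this model. It is optional and exploratory, and the output that the protocol commits to is descriptive. Section 11 calls itself a general description. Protocol 11.7 and SAP 7.4 place the exposure-response work in separate plans, and those and the Part 2 SAP are not available here. All of that stands, and it limits severity. It does not make the stated terms fit the sponsor's own data.

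A second reply is that scale, more than the missing term, drives the misfit. This is largely right: the log ratio alone removes most of it. But 11.6 specifies change from baseline, and up to about 13% per cell remains if the effect is dose-proportional.

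A third reply is that the 36% figure pairs 0.3 mg/kg with the highest Phase 1 dose, 2.5 mg/kg, which lies above this study's 1.8 mg/kg ceiling. That is fair. The 36% shows the direction and mechanism and does not predict the error at the planned doses.

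A reader might also infer more than the documents support:

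- That all the least-squares means are wrong. The text does not say which are meant, and means by dose or by visit are unbiased with balanced data.
- That the error is largest at the lowest dose at Week 5. This holds for relative error. In absolute terms other cells are as bad or worse: under (a), 1.28 at 1.2 mg/kg, 1 h, against 0.72 at 0.3 mg/kg, Week 5.
- That TT would appear shortened. The negative fit depends on the assumed dose-effect relation; under the Emax assumptions the fit stays positive.
- That aPTT and PT are shown to behave the same way. Protocol 1.1.2.2.4 gives only their maximum increases. The unequal fall is inferred from the PK and overall summary sections.
- That dose decisions rest on this output. PD data are among the inputs to dose selection and adaptation, but no passage says that these least-squares means are used.

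**Conclusion.** Wrong as written, of minor severity. On the raw change scale the model in 11.6 imposes a common fall that the protocol's Phase 1 TT data contradict (about 1.0 x baseline at 0.3 mg/kg, at least 2.0 x at the highest dose). Dose-at-visit least-squares means would be biased: 0.45 against 0.70 at 0.3 mg/kg on Day 14 from the documents' own figures. At the planned doses the largest relative error is expected at the lowest dose at late visits. Its size rests on extrapolation, with Week 5 at 0.3 mg/kg fitted as 0.07 against 0.41 or -0.33 against 0.39 depending on the concentration-effect assumption. The conclusion applies only if means are reported by dose at each visit on the raw scale.

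**What to change.** In Protocol 11.6, and in the separate PK/PD plan, add a dose-by-visit fixed effect, preferably with log ratio to baseline as the response, and state that least-squares means with 95% CIs are reported for each dose at each visit. With the interaction, the model reproduces the cell means exactly when data are complete.

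The interaction uses (3 - 1) x (3 - 1) = 4 degrees of freedom with three doses and (4 - 1) x (3 - 1) = 6 with four, and intervals become slightly wider. No new data are needed.

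A baseline covariate and a right-censoring rule for TT above the reporting limit are optional refinements. Neither is shown to be needed: the gain from the covariate is not quantified, and the 120-second limit was described only for Phase 1 doses above this study's ceiling.

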- ^s Pharmacodynamic evaluations will include the coagulation assays (ie, thrombin time [TT], ecarin clotting time [ECT], prothrombin time [PT], and activated partial thromboplastin time [aPTT]). Samples on Day 1 will be obtained before the study drug is administered and at 1 hour after the start of the study drug infusion.
- ^t All adverse events, whether serious or nonserious, will be reported from the time a signed and dated informed consent form (ICF) is obtained until the completion of the subject's last study-related procedure. Adverse events of special interest are bleeding events, infusion reactions, hypersensitivity reactions, and wound or joint complications). All suspected symptomatic efficacy (thrombotic) events will also be captured as adverse events of special interest.

ABBREVIATIONS

ADA	antidrug antibody
aPTT	activated partial thromboplastin time
AV	arteriovenous
CEC	Clinical Events Committee
CI	confidence interval
CSR	clinical study report
СТ	computed tomography
CYP	cvtochrome P450
DOAC	direct-acting oral anticoagulants
DVT	deen vein thrombosis
ECG	electrocardiogram
eCRF	electronic case report form
FCT	ecarin clotting time
eDC	electronic data canture
FOD	end of doging
EOD FeCl	ferric chloride
FCU	folliele stimulating hormone
FVa	Factor Va
CCP	Cood Clinical Practice
CLD	Good Laboratory Practice
ULF	Usedesha and Neurological Deficits with corebrashing fluid Lymphoxytopic
	headache and Neurological Denens with cereorospinal fluid Lymphocytosis
	Investigator's Drashura
ID	informed concerns forme
	Informed consent form
	International Conference on Harmonisation
IDMC	Independent Data Monitoring Committee
IEC	immunoglohin
	Infinunogiooni
	Investigational Product Preparation Instructions
IKD	intent to treat
	intent to treat
	intravenous
	low malacular weight hangerin
	iow molecular-weight hepatin
MCP-MOd	Multiple comparison procedure and modeling
MedDKA	Medical Dictionary for Regulatory Activities
MI	myocardial infarction
NI	noninteriority
NSAID	nonsteroidal anti-inflammatory drug
OC DCC	Operations Committee
PCC	prothrombin complex concentrate
PD	pnarmacodynamic(s)
PE	Pulmonary embolism
P-gp	P-glycoprotein
PK	pharmacokinetic(s)
PQC	product quality complaint
	OT compared a complimente Dei logice de Compute
QICF	Q1 corrected according to Friderica's formula
KBU	rea blood cell
SAD	single-ascending dose
SAP	statistical analysis plan
SU SD	Steering Committee
SD	standard deviation
SMQ	standardized MedDKA queries
SQ	subcutaneous

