9.4. Pharmacodynamic/Biomarker Evaluations

All subjects will have plasma samples collected to assess PD markers as specified in the Time and Events Schedule. The assay plan is designed to assess target engagement and the mechanism of action with a battery of PD assessments. Pharmacodynamic evaluations will include the coagulation assays (ie, TT, ECT, PT, aPTT) and a D-dimer assessment. Subjects who experience a bleeding event or symptomatic thrombotic event should have PD samples (except D-dimer) collected as soon as practically possible after the event occurs. Samples on Day 1 will be obtained before the study drug is administered and at 1 hour after the start of the IV infusion and all assays will be performed by a central specialty laboratory. Additional information about the collection, processing, storage, and shipment of PD samples will be provided in a separate laboratory manual. It is expected that apixaban would have no effect or minimal effects on all of the coagulation assays and therefore, analysis of the apixaban samples is not planned.

To maintain the blind of the study, the investigator should not measure coagulation assays locally unless considered necessary for subject clinical care. In addition, the investigator will not receive the results of the PD parameters from the central specialty laboratory during the conduct of the study.

Thrombin Time

The thrombin clotting time (designated TT) is a simple test that measures the time for clot formation in citrated plasma after the addition of thrombin. It reflects the effect of thrombin to cleave fibrinogen to form fibrin. Heparin and direct thrombin inhibitors such as hirudin, argatroban, and dabigatran are inhibitory, LMWH is partially inhibitory, and apixaban is inactive.

Ecarin Clotting Time

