2.7. Baseline and Endpoint

Baseline is defined as the last observation prior to the start of the first study agent administration or randomization date.

Endpoint is defined as the last available postbaseline result within the analysis period. Unscheduled visit results are included in this definition and will be considered as the endpoint value if the unscheduled visit result is the last postbaseline result available within the analysis period. The result refers to an event.

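### The optional PD mixed model for change from baseline leaves out the predose value as a covariate; adding it costs little and may make the least-squares means more precise

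*Protocol*

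**What the plan says.** Protocol section 11.6 first makes the analysis optional: "The parameters of TT, PT, and aPTT may be statistically analyzed using mixed models". It then lists the terms: "The mixed model for the change from baseline PD parameters will include dose and visit as fixed effects and subjects as random effects". The promised output is equally specific: "The least-squares means for change from baseline and associated 95% CIs will be provided". Other PD parameters, which would include ECT and D-dimer, may be handled in the same way.

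The predose value that could serve as a covariate is already planned. Section 9.4 says "All subjects will have plasma samples collected to assess PD markers", and on timing, "Samples on Day 1 will be obtained before the study drug is administered and at 1 hour after the start of the IV infusion". The Time and Events Schedule adds coagulation samples at the Day 10-14 visit and Week 5. Section 9.4 also says that "analysis of the apixaban samples is not planned", so the model covers the JNJ-64179375 doses only.

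The Part 1 SAP does not add the term. Its section 2.7 defines the reference value: "Baseline is defined as the last observation prior to the start of the first study agent administration or randomization date". Section 7.3 describes sampling. Section 7.4 mentions mixed effects models for the PK/PD relationship and leaves the details to a separate document.

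**The concern.** A change score subtracts the whole baseline value, which amounts to assuming that post-dose values rise one for one with baseline. If the true slope differs from 1, the change carries avoidable noise, and a chance difference in baseline between doses passes into the least-squares means.

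There is reason to doubt a slope of 1 here. The baseline is drawn the day after knee replacement, and two of the three scheduled post-dose samples come at Day 10-14 and Week 5, when the effect of surgery may have faded.

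What is at stake is modest. One exploratory objective is to judge which assay best measures the drug's effect. The Phase 1 summary in Protocol section 1.1.2.2.4 gives maximum prolongations of about 1.3-fold for PT and 1.6-fold for aPTT, against about 7-fold for TT at the top doses. Extra noise would matter more for the first two.

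**Working it through.** The documents state no sample size, power or precision for this model, so there is no figure to reproduce. The check compares residual variances.

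**Inputs.** The model terms, the optional status and the output come from Protocol 11.6, and the predose sample from 9.4. Protocol 3.1.1 gives three planned Part 1 doses with about 40 JNJ-64179375 subjects each. The baseline SD (s0), the post-dose SD (s1) and their correlation (rho) are not given. All three are assumptions and are shown over a range.

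**Step 1: direction.**
- Change score: variance = s0² + s1² − 2·rho·s0·s1.
- Baseline as covariate: variance = s1²(1 − rho²).
- Difference = s0² − 2·rho·s0·s1 + rho²·s1² = (s0 − rho·s1)².

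A square is never negative. Apart from the small cost of estimating the slope, adjustment cannot raise the residual variance. It gains nothing only when the slope rho·s1/s0 equals 1.

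**Step 2: equal SDs, one post-dose visit.** For a dose contrast the ratio is (1 − rho²)/[2(1 − rho)] = (1 + rho)/2. For a least-squares mean with K doses, evaluated at the overall mean baseline, it is [(1 + rho) + (1 − rho)/K]/2.

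| rho | Change variance | Adjusted variance | Contrast ratio | Least-squares mean ratio, K = 3 |
|---|---|---|---|---|
| 0.3 | 1.40 | 0.91 | 0.65 | 0.77 |
| 0.5 | 1.00 | 0.75 | 0.75 | 0.83 |
| 0.7 | 0.60 | 0.51 | 0.85 | 0.90 |

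Variances are in units of the common single-time variance.

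**Step 3: unequal SDs, one visit.** With k = s1/s0 the contrast ratio is k²(1 − rho²)/(1 + k² − 2·rho·k). As an illustration, suppose the SD scales with the mean and take the Phase 1 maxima, k = 1.3 for PT and 1.6 for aPTT.

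| k | rho 0.3 | rho 0.5 | rho 0.7 | rho 0.9 |
|---|---|---|---|---|
| 1.3 | 0.81 | 0.91 | 0.99 | 0.92 |
| 1.6 | 0.90 | 0.98 | 0.99 | 0.72 |
| 5 | 0.99 | 0.89 | 0.67 | 0.28 |

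For k = 1.6 and rho = 0.5: 2.56 × 0.75 / (1 + 2.56 − 1.6) = 1.92/1.96 = 0.98. The slope there is 0.5 × 1.6 = 0.8, already near 1, so little is left to gain.

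**Step 4: several visits.** A simulation with 4,000 runs, equal SDs, 3 doses of 40 subjects, 3 post-dose visits and a random intercept gave these ratios of adjusted to unadjusted variance:

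| rho | Least-squares mean | Dose contrast |
|---|---|---|
| 0.3 | 0.64 | 0.46 |
| 0.5 | 0.77 | 0.65 |
| 0.7 | 0.85 | 0.80 |
| 0.9 | 0.94 | 0.93 |

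The direction is therefore settled. The size runs from nil to large, depending on values the documents do not give.

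**The case against.** The best reply has three parts. First, the analysis is optional, the PD endpoints are exploratory, and no PD hypothesis or precision target exists. Second, Protocol section 11 presents itself as a general outline, SAP 7.4 defers PK and PD detail to a document not supplied, and a separate Part 2 SAP is to follow; any of these could add the covariate. The list of terms in 11.6 also omits a dose-by-visit term and a covariance structure, so it may not be complete. Third, no decision is shown to turn on a slightly narrower interval, and the choice of assay will also draw on the PK/PD work.

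All of this limits the importance of the point. It does not remove it, because an analyst who follows 11.6 as written would leave the covariate out.

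Three stronger readings are tempting, and the documents do not support them.
- A reader might infer a reliable variance cut of 15% to 35%, or a rise in power from 80% to about 90% at rho = 0.5 (86% at rho = 0.7). Those figures need equal SDs and concern dose contrasts. Section 11.6 plans least-squares means with intervals, not contrasts, and with k = 1.6 the gain at those correlations is 1% to 2%.
- A reader might infer bias. Change from baseline is a valid measure when doses are randomised in parallel, as in Part 2. In Part 1 the doses come in successive cohorts, so the argument about chance imbalance is cleanest in Part 2.
- A reader might infer that low correlation with baseline is established. The 1-hour sample could correlate well with the predose value.

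**Conclusion.** The point holds as a minor efficiency improvement. The model in section 11.6 omits a covariate that is scheduled to be collected for every subject, and including it cannot raise residual variance in large samples.

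The benefit is conditional. It is worthwhile if the SDs are similar and the correlation is low to moderate, and close to nil where the slope on baseline is near 1. For TT the gain is better described as less consequential, given its large drug effect, than as necessarily small: at k = 5 and rho = 0.7 the contrast ratio is 0.67. Confidence in the direction is high; confidence in the size is low.

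**What to change.** In Protocol 11.6, add the predose value of the parameter as a fixed covariate, with a baseline-by-visit term, for TT, PT, aPTT and any other PD parameter analysed this way. The interaction lets the slope differ between 1 hour, Day 10-14 and Week 5. Report the least-squares means at a common mean baseline. Carry the same wording into the separate PK/PD analysis plan; if that plan already includes the covariate, align 11.6 with it.

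The cost is two model terms and a few degrees of freedom. No new data are needed, and no subject is lost, since anyone without a predose value already has no change score.
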